### **4.0 RESEARCH PLAN AND DATA COLLECTION**

The goal of this proposal is to evaluate if the use of NGS on preoperative antibiotic selection reduces postoperative infection rates over the standard of care. Patients scheduled to receive a transurethral procedure, such as a ureteroscopy or percutaneous nephrolithotomy (PCNL), will be approached for enrollment prior to their procedure. After informed consent has been obtained, approximately 5-10 mL of left-over urine, collected for a standard of care urine culture, will be obtained for research and sent to MicroGen Dx for NGS. Patients will be randomized to receive either standard of care culture results (only), versus NGS results and Infectious Disease (ID) Pharmacist antibiotic recommendation. The physician will utilize these results to select the best antibiotic for the case but is not required to abide by the ID pharmacist's recommendation. The standard of care group will also have a urine sample sent to MicroGen Dx, but the results will not be provided to the physician. All subjects enrolled will receive a standard of care culture as part of routine care. A chart review and/or telephone follow up will be completed approximately 7-14 days post urologic procedure to assess for complications, infections related to the procedure, and antibiotics prescribed.

The treating physicians will have control over antibiotic administration. Their determination, interaction, and ultimately patient outcome will be documented and evaluated. As a result, the treating physicians will be considered participants in this study. A waiver of documentation of informed consent for the treating physicians will be included. In addition, an information sheet will be provided to treating physicians specifically.

Subjects will be recruited from approved Urology clinics at time of their preoperative appointment, approximately 30 days, but up to 90 days, prior to the planned transurethral procedure. Patients with ureteral stents will not be excluded; therefore, essentially any patient going to surgery for percutaneous nephrolithotomy, ureteroscopy or other transurethral procedure, within two to four weeks will be screened for eligibility and approached for enrollment. In the event the standard of care urine culture was performed more than 45 days before the urologic procedure; the treating physician will ask the patient to provide an additional urine sample as part of normal practice. Research staff will obtain a second sample (5-10 mL) of left-over urine, which will then be sent to MicroGen Dx for analysis. If this occurs, the second sample will be used for analysis.

**Next Generation Sequencing:** Approximately 30-50 mL voided whole urine will be collected as per routine care. Approximately 5-10mL of left-over urine will be obtained for research, placed in special vacutainers supplied by MicroGen DX, a CAP accredited and CLIA licensed clinical diagnostic lab, and sent for analysis. MicroGen DX will perform rapid PCR for common resistance genes prior to transurethral procedure, such as ureteroscopy or percutaneous nephrolithotomy. NGS results will be available within 48-72 hours. Additionally, NGS analysis will be performed on available or leftover urinary stones for a proportion of the subjects.

Target bacterial or fungi DNA on the quantitative PCR (qPCR) panel assay on the Roche LightCycler 480 II instrument and sequencing of 16S ribosomal RNA hypervariable regions V1-V2 using Ion Torrent (Ion Torrent PGM) will be run.

**Data Collection:** Prior to and after surgery, patient medical history, demographics, pre and post-surgical antibiotic treatment plans, and speciation results from the urine culture will be collected by research staff. Results obtained from the NGS/PCR analysis report, such as resistance gene data, will be recorded. Recommendations from the ID pharmacist will also be recorded.

**Case Study Creation:** ID pharmacist will be provided with the NGS report and relevant de-identified clinical data, such as weight and allergy history, to decide the appropriate antibiotic treatment course for the intervention group. The treating physician will be provided with both NGS report and ID pharmacist recommendations to utilize these results to select the best antibiotic for the case, but is not required to abide by the ID pharmacist's recommendation. Subjects assigned to the standard of care group will have urine cultures sent for analysis, and the treating physician will choose antibiotics based on results as per usual practice. The treating physician will not receive NGS report or ID pharmacist recommendations for standard of care group.

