### **3.0 SPECIFIC AIMS**

#### **Specific Aim 1: To perform a randomized clinical trial investigating the use of NGS for antibiotic selection to lower post-operative infection rates over the standard of care.**

*Hypothesis: utilization of NGS for the selection of preoperative antibiotics reduces postoperative infection rates by 75%. Our baseline rate of infection was 11-15% in our pilot study and nearly 5-10% in our investigation of those ureteroscopies (not PCNL, which has a higher rate) of infections at a university hospital. We expect with the correct antibiotics that the infection rate may drop from 11% to 1% or less. The control arm will be utilized to determine if NGS may have predicted infections or high-risk groups. Retrospective databases include anywhere from 2-15% of patients will present with a postoperative infection after transurethral surgery. Current prophylaxis strategies do not always follow guidelines, and with concerns over current non-reimbursement for infectious complications, surgeons may be using more antibiotics.*

**Specific Aim 2: Accuracy of NGS and PCR compared to standard urine culture prior to transurethral procedures.** *Hypothesis: NGS can identify 50% of negative urine cultures that could harbor uropathogenic bacteria.* We anticipate a substantial number of patients have uropathogenic bacteria present yet are not detected by traditional approaches. We seek to expand our investigation on this topic in order to understand how best to interpret the results and present them to physicians. All participants will have both a standard of care urine culture and NGS testing/ID Pharmacy review for comparative analysis. Only subjects assigned to the NGS group (n=110) will have NGS urine culture results and ID Pharmacist recommendations shared with the physician to determine antibiotic selection. Operating characteristics to include sensitivity, specificity, positive, and negative predictive value will then be performed and area under the receiver operative curve calculated. We will enroll a minimum of 250 patients and 5 urology provider-participants into this study. We anticipate that 20 of the patients will have positive urine cultures and 200 will have negative cultures. Of the 200 negative cultures we anticipate that 100 (50%) will harbor uropathogenic bacteria which will be identified via NGS.

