## **8.4 Randomization (research)**

A randomization list will be generated using a computer-based-random number generator [www.randomizer.org](http://www.randomizer.org). Randomization will be created 1:1, n=110 per group. Once created, individual envelopes will be created, and study staff will pull an envelope after the participant signs consent. The research staff will not be blinded to the randomization groups. The standard of care group will have urine culture results directed to treating physician. The intervention group will have NGS results sent to Infectious Disease pharmacist, [name] to provide an antibiotic recommendation. The antibiotic recommendation, along with NGS results, will then be provided to treating physician. The physician will then utilize these tools to select the best antibiotic for the case but is not required to abide by the ID pharmacist's recommendation. The standard of care group will have a urine sample sent to MicroGen Dx, but the results will not be provided to the physician.

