### **10.0 METHOD OF ANALYSIS/STATISTICS**

**Next Generation Sequencing:** Standard of care whole urine will be collected (approximately 30-50 mL) utilizing special vacutainers supplied by MicroGen Dx. Approximately 5-10mL of urine taken for culture will be sent to MicroGen Dx, a CAP-accredited and CLIA licensed clinical diagnostic lab, for analysis. MicroGen Dx will perform rapid PCR for common resistance genes prior to ureteroscopy or percutaneous nephrolithotomy. The plan will be to run target bacterial or fungi DNA on the quantitative PCR (qPCR) panel assay on the Roche LightCycler 480 II instrument and sequencing of 16S ribosomal RNA hypervariable regions V1-V2 using Ion Torrent (Ion Torrent PGM).

**Microbiome:** Sequencing reads were demultiplexed using QIIME2 software and denoised using dada2 software, using a phred score threshold of 28. Alpha diversity will be measured using the Shannon index, and a Wilcoxon test was used to determine whether the Shannon index differed between patients with stents and those without stents at the time of urine collection. Principle coordinates analysis (PCoA) of Bray-Curtis dissimilarity will be performed to visualize differences in species composition between patients with and without stents, and Linear discriminant analysis Effect Size (LEfSe) analysis was conducted to identify differentially abundant taxa between stent and non-stent groups.

**Sample size:** This will be a randomized trial of Microgen Dx versus standard of care. The primary endpoint is infection within 14 days of surgery. The primary objective of the study is to evaluate whether Microgen Dx reduces an infection rate compared to the standard of care. The null hypothesis is that infection rates within 14 days of surgery are the same between the randomization arms. The alternative hypothesis is that infection

rates within 14 days of surgery are not equal between the randomization arms. The infection rates are assumed to be 11% in the control arm and 1% in the experimental arm based on our preliminary data. A sample size of 85 per group will give 80% power to detect a 10% difference in infection rate when the two-sided Z-test with alpha=0.05 is used. Demographics and potential confounding factors will be summarized by randomization arm. A logistic regression model will be used to measure the association between the primary outcome and treatment arm with adjustment for the observed covariates.

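### No step keeps control-arm NGS/PCR results from the research staff who assess infection, so the Aim 1 check of whether NGS predicted infection is open to review bias

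*Combined protocol and SAP*

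**What the plan says.** Section 3.0, Specific Aim 1, gives the control arm a second use beside the randomised comparison: "The control arm will be utilized to determine if NGS may have predicted infections or high-risk groups". Section 10.0 sets out no analysis for this.

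Section 4.0 sends control-arm urine for sequencing and adds "but the results will not be provided to the physician". Section 8.4 repeats the restriction, and no section extends it beyond the physician. On recording, Section 4.0 says "Results obtained from the NGS/PCR analysis report, such as resistance gene data, will be recorded". That sentence names no person and no date. It follows a sentence giving the collection of history, antibiotic and culture data to research staff, before and after surgery.

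Section 10.0 states: "The primary endpoint is infection within 14 days of surgery". No section gives criteria for infection, a masked assessor or adjudication. Under Sections 1.0 and 8.7, research or study staff ask about infection by telephone and/or review the chart about 7 to 14 days after surgery. Section 8.8 adds a further chart check for missed infections and names no reviewer. Section 8.4 says "The research staff will not be blinded to the randomization groups". That sentence concerns knowledge of the arm and says nothing either way about knowledge of the NGS result.

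**The concern.** The control arm is the only group in which NGS can be related to infection without the result having been acted on. For that comparison NGS is the index test and infection is the outcome. If the assessor knows the test result, an ambiguous report such as mild fever, urinary symptoms or an extra antibiotic course may be pursued further, or counted more readily, in a patient known to carry an organism. Infections then collect among NGS-positive patients for reasons unrelated to biology, and the association and apparent sensitivity are overstated.

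This differs from staff knowing the arm. All patients in this check are controls, so the question is whether the assessor knows which controls were NGS-positive. Masking the arm alone would not necessarily hide that. Once outcomes have been assessed with the result known, the masking cannot be restored.

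**Working it through.** **The plan's own figure.** Section 10.0 states "The infection rates are assumed to be 11% in the control arm and 1% in the experimental arm based on our preliminary data" and "A sample size of 85 per group will give 80% power to detect a 10% difference in infection rate", where the "two-sided Z-test with alpha=0.05 is used". The unpooled formula gives n = (1.960 + 0.842)² × [0.11 × 0.89 + 0.01 × 0.99] / 0.10² = 7.849 × 0.1078 / 0.01 = 84.6, so 85 per group. The figure reproduces, and nothing below changes it.

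**Does the NGS result exist before infection is assessed?**
- Urine is taken about 30 days before surgery (Section 1.0).
- Results come in 48 to 72 hours (Section 4.0). Counted from collection, that is about 27 to 28 days before surgery.
- Infection is assessed about 7 to 14 days after surgery (Section 8.7).
- The gap is therefore about 27 + 7 = 34 to 28 + 14 = 42 days. Section 6.0 allows other intervals up to 45 days, but even a sample taken the day before surgery would be reported by about day 2, before the first assessment.

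**Could staff link a report to a patient?** Samples go out under a subject ID (Section 8.2), and the principal investigator and approved research staff hold the identifiers (Section 7.0). So they could, and no rule delays it.

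**How many infections carry the check?** With 110 controls (Section 8.4) at 11%, 110 × 0.11 = 12.1. At the other arm sizes that the plan's totals imply, the count is 9.4 (85 per arm), 13.8 (125) or 16.5 (150).

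**How many controls are NGS-positive?** Aim 2 expects 20 positive and 200 negative cultures, with 100 of the negatives NGS-positive.
- Counting only those 100: 110 × 100/220 = 50.
- Counting the 20 culture-positive patients as NGS-positive too: 110 × 120/220 = 60. The pilot in Section 2.0 supports this, since NGS agreed with both positive cultures.

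**Illustration.** Assume no true link, all infections found in NGS-positive controls, and a fraction d found in NGS-negative controls. The values of d are assumptions; the documents give none.
- Apparent risk ratio = 1/d.
- Apparent sensitivity = P / (P + N × d), where P and N are the numbers NGS-positive and NGS-negative.

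| d | Risk ratio | Sensitivity, P = 50, N = 60 | Sensitivity, P = 60, N = 50 |
|---|---|---|---|
| 1.00 | 1.00 | 50/110 = 45% | 60/110 = 55% |
| 0.75 | 1.33 | 50/95 = 53% | 60/97.5 = 62% |
| 0.50 | 2.00 | 50/80 = 63% | 60/85 = 71% |

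**In whole patients.** Take 12 infections, 6 in each of two groups of 55. Two extra borderline events counted among NGS-positive patients give 8 against 6: risk ratio 1.33, sensitivity 8/14 = 57%. If two are also dropped among NGS-negative patients, it is 8 against 4: risk ratio 2.0, sensitivity 8/12 = 67%.

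**The case against.** The strongest reply is that the sequence is inferred. A reader might conclude that control reports reach staff before surgery and that the same people then decide who was infected. The documents do not say so: no section states who receives control reports, when they are opened, or that one individual does both tasks. A reader might also infer that control results leak to the surgeons through staff who deliver the intervention-arm reports, but Sections 8.4 and 8.6 do not say who delivers them. This objection stands against those readings. It does not remove the gap, because the bias needs only that the result is seen before infection is judged, and nothing prevents that.

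Second, infections charted by treating physicians, who do not see control NGS results, are less exposed, and Section 8.8 adds a chart check. This stands in part. Follow-up may be by telephone, and under Section 8.7 staff alert the medical team to infections they find, so a staff enquiry can itself lead to a chart entry. The Section 8.8 check is not described as masked.

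Third, it would go too far to say that ascertainment alone would establish NGS as a predictor. With P = 50 and N = 60, the expected counts are 5.5/50 against 4.95/60, or against 3.3/60. The approximate 95% intervals are 0.42 to 4.2 around 1.33 and 0.54 to 7.4 around 2.0, and both include 1. What remains is a biased estimate resting on few events.

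Fourth, the affected analysis is one sentence under Aim 1, and the undefined endpoint is the wider problem. That is fair, and it limits the weight of the point. Written criteria and an assessor masked to NGS results would also address it.

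**Conclusion.** The point holds as a gap in the plan. Control-arm NGS/PCR results are withheld from the physician only, they normally exist weeks before infection is assessed, and infection is judged by research staff without stated criteria or masking. The Aim 1 check of NGS as a predictor is therefore open to review bias.

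Under the assumed detection rates the apparent risk ratio is 1.33 to 2.0 with no true link, and apparent sensitivity rises by about 7 to 17 percentage points, depending on how many controls are NGS-positive. These figures show what could happen; they do not estimate what will. With about 12 events, a few judgement calls would suffice.

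A reader might extend this to the primary result or to test accuracy, but the documents do not support that. The distortion described is in how control infections divide between NGS-positive and NGS-negative patients, whereas the randomised comparison uses arm totals; staff knowledge of the arm is a separate question. Aim 2 compares NGS with urine culture, so infection ascertainment does not enter it. This is an inexpensive improvement to a secondary use of the data and does not challenge the main design.

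**What to change.** In Sections 4.0 and 8.4, state that control-arm NGS/PCR reports are held by the laboratory, or kept unopened by anyone who assesses outcomes, until that patient's infection outcome form is completed and locked, and are entered in the database only then. Apply the same rule to any pharmacist review of control results, since Aim 2 refers to such a review for all participants.

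The cost is one instruction to the laboratory and one line in the protocol. The downside is that control-arm NGS data arrive later. Care stays as planned: the treating physician already does not receive these results, and no section uses them for care or for the quarterly safety review in Section 11.0.

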## 5.0 INCLUSION AND EXCLUSION CRITERIA

Patients:

Eligibility Criteria

- 5.1 Patients planning to undergo kidney or bladder stone removal surgery using endoscopy including ureteroscopy and percutaneous nephrolithotomy or any other transurethral procedure
- 5.2 Be age 18 or older
- 5.3 Be able to give informed consent

Exclusion Criteria

- 5.4 Unable or unwilling to provide informed consent
- 5.5 Age <18
- 5.6 Does not meet inclusion criteria

Physicians:  
Eligibility Criteria

5.1 Treating Physician within the Urology Clinic  
 5.2 Has a patient that is eligible to participate in this research study

## 6.0 STUDY CALENDAR

Study Visit	Visit 1	Visit 2	Visit 3	Visit 4
	Baseline	Urine collection	Transurethral Procedure (day of surgery)	Follow-up
Timeline	Day 1	Up to 90 days from V1	W/in 45 days of urine collection	Approx. 7-14 days post-surgery
Informed Consent	R			
Demographics	R			
Medical History	R	R		R
SOC Urine culture	-----SOC  -----			
Whole Urine collection	-----R  -----			
Randomization	-----R  -----			
NGS Analysis of Urine Culture	-----R  -----			
Results of NGS to Physician	-----R  -----			
Antibiotic Prophylaxis	-----SOC  -----			
Additional Antibiotics as needed	-----SOC  -----			
Provider-Participant Questionnaire/Survey	-----R  -----			
Urologic Stone Procedure			SOC	
Urologic stone collection			R*	
Chart Review and/or telephone follow up	R 	R 	R 	R 
Adverse Events	R	R	R	R

 Indicated procedures may be completed at time of baseline or visit 2, up to 90 days from enrollment  
 Indicated procedures may be repeated if SOC urine culture is not completed within 45 days of procedure  
 Patient assessments may be completed over the phone  
 \*Any extra or leftover stone(s) available will be collected and sent to MicroGen DX for analysis

## 7.0 SCREENING AND RECRUITMENT

Patients will be identified and recruited through Urology outpatient clinics located at the Medical Arts and Research Center (MARC), University Hospital System (UHS), and the South Texas Veterans Healthcare System Audie L. Murphy Hospital in the genitourinary (GU) clinic. Eligible patients will be approached at the time of their standard of care visit. The inclusion of subjects, or refusal to participate in this study, will not affect the health care they will receive.

Once a subject is identified who may meet eligibility criteria, the provider and/or approved research staff will explain to each potential subject the research purpose, voluntary nature of participation, study procedures, risks and benefits of participation, alternatives available and the subjects' rights and responsibilities. The informed consent process will be carried out by personnel who are IRB trained and designated for that role. There is no waiting period required before enrolling. The participant may decline to

participate, decide to participate, or take the consent home to think about participating. Subjects will consent in a private room, and usual privacy policy practices followed. Study procedures and objectives will be described to them, and they will be given a copy of the informed consent document. Subjects will also be given contact information for someone they can call with any questions. No study procedures will occur until the patient has signed the informed consent.

Remote Consent/Waiver of documentation of informed consent: Eligible subjects undergoing standard of care visits via telephone, video conference or telemedicine will be consented remotely in the absence of face-to-face contact. The purpose of remote consent is to allow the study investigator/designee and potential subject to engage in the informed consent process similar to what would be conducted face-to-face under normal circumstances. Initially, subjects will be introduced to the study by urology provider and explain the consent process. Subjects will be informed that a consent form will be sent via e-mail, mail or fax. Following delivery of the consent form, approved research staff will call subject and conduct the consent interview via telephone when the subject can read the consent form during the discussion. Research staff will confirm subject's name and date of birth from subject before discussion to ensure the identity of the subject. If agreed to participate, subject will provide verbal consent. No study procedures will occur until the subject and research staff have provided verbal consent.

Each participant will be assigned a unique subject identifier (subject ID) that has no meaning external to the study database. The participant identifiers will be further masked and password protected, and stored only on a secure server behind a "firewall." Only the PI of the IRB approved protocol ([name]) and approved research staff will have access to these identifiers. A research study file will be kept for each participant accrued. This file will include the participant's consent, the assigned unique subject identifier, research records, and copies of relevant source documents. All participant records will be securely stored in the Urology research offices. A data entry system will be prepared in RedCap, Excel, or equivalent software interface for the study. Both the subject identifier and sequence number for each patient will be entered into the database together with clinical outcome data collected across visits.

For the providers, all providers within the Department of Urology who perform urologic stone procedures (n=5) will be sent an email, informing them about the research study. These providers will also be approached in person with an information sheet. Prior to study entry, approved study staff will explain to each potential provider-participant the research purpose, voluntary nature of participation, study procedures, risks and benefits of participation, and their rights and responsibilities as participants. The informed consent process will be carried out by personnel who are IRB trained and designated for that role. No study procedures will occur until the provider-participant has provided verbal informed consent, which will be documented with a research note by a member of the research team.

No identifiable information will be collected about or from provider-participants. Surveys completed by provider participants will be stored within the specific subject's (i.e. patient's) research record.

